Clinical Efficacy Analysis of Resveratrol in the Treatment of Primary Ovarian Insufficiency

Date: May 16, 2022

Research Proposal Summary

Scheme number	LCYJ-B05
Scheme name	Clinical effect of resveratrol on early onset ovarian insufficiency
Version number/date	Version 2.1, May 16, 2022
Indications	POI
Test purpose	In order to evaluate the role of resveratrol in the occurrence and development of a variety of ROS-related diseases including POI/POF, and to clarify the clinical effect and mechanism of resveratrol antioxidant therapy.
Research design	Prospective, multicenter, randomized, controlled clinical trial design
Total number of cases	150
Number of research centers	4
Study period	36 months
Research object	Diagnostic criteria : The diagnostic criteria for premature ovarian insufficiency (POI) refer to the “2017 Chinese Expert Consensus on Clinical Diagnosis and Treatment of Premature Ovarian Insufficiency” and “2016 Expert Consensus on Hormone Supplementation Therapy for Premature Ovarian

Insufficiency”; including: (1) Age <40 years old; (2) oligomenorrhea or amenorrhea for at least 4 months; (3) at least 2 times serum basal follicle-stimulating hormone (FSH) >25IU/L (interval > 4 weeks). Subclinical POI: FSH level is 15~25 IU/L, which is a high-risk group.

The diagnostic criteria for premature ovarian failure (POF) refer to the “2017 Chinese Expert Consensus on Clinical Diagnosis and Treatment of Premature Ovarian Insufficiency”, which refers to amenorrhea, FSH>40IU/L, and decreased estrogen levels before the age of 40, accompanied by varying degrees of perimenopause Stage symptoms are the terminal stage of POI.

standard constrain:

1. Amenorrhea or oligomenorrhea at least 4 months and two (>4 weeks interval) basal FSH \geq 10mIU/ml;
2. age<40 years old;
3. Informed consent, voluntary experiment.

Exclusion criteria:

1. Pregnant and lactating patients;
2. Patients with endometriosis, adenomyosis, endometrial lesions (submucosal fibroids ,endometrial polyps, etc.) , uterine fibroids>4 cm or hysterectomy;
3. Patients with adrenal cortical hyperplasia or tumor;
4. Ovarian neoplasms patients;
5. Hydrosalpinx patients;
6. Hyperprolactinemia patients;
7. Patients who are participating in other clinical trials or

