	
have participated in other clinical trials within the past three months;
 
8. Patients with suspected or real history of alcohol and drug abuse;
 
9. Known allergy to the investigational drug or its components;
 
10. Other patients deemed unsuitable for participation in this trial by the investigator.
 
Note: Patients who were receiving hormone replacement therapy at the time of recruitment were required to take at least a 3-month suspension of medication to participate in this trial.

Trial grouping and medication
	
1. POI patients group: According to the computer-generated random sequence, eligible patients were randomly assigned to the RES group and non-RES group according to 1: 1. POI IVF patients were divided into two groups: the RES treatment group (group A) and the non-RES treatment group (group B). Basal sex hormone and anti-Muller tube hormone were administered on day 2/3 of the menstrual cycle before treatment and 3 months after treatment. Antral Follicle (AFC) was detected by transvaginal B-ultrasonography, and basic sex hormones included follicle-stimulating hormone (FSH), Luteinizing hormone (LH), Estradiol 2 (E₂) and Testosterone (T).
 
2. Medication: Patients in group A received oral RES at 250mg daily for three months, and those in the non-RES group received oral vitamin E at 100mg daily for three months.

Treatment and follow-up
	
Course of treatment: Patients in group A received oral RES at 250mg daily for three months, and those in the non-RES group received oral vitamin E at 100mg daily for three months. All patients used microstimulation to superstimulate ovulation, and

clomiphene 50-150mg was taken orally from the 3rd to 5th day of menstruation, once a day for a total of 5 days later, the sex hormones and follicular diameter were checked, and 150-300IU Gonadotropin (Gn) was added as appropriate to the night needle day. After follicle maturation, 10000IU of Human Chorionic Gonadotropin (HCG) was injected intramuscularly or 250ug Ovidrel subcutaneously to induce ovulation. 36-38 hours later, a vaginal ultrasound-guided puncture was performed to collect eggs.

Specific inspection items include:

1. The patient's hormone levels (basal FSH, LH, E2, T) were detected on day 2/3 of the menstrual cycle;
2. Anti-Mullerian hormone (AMH) was detected in patients on day 2/3 of the menstrual cycle;
3. The numbers of antral follicles (AFC) were recorded by B ultrasound transvaginal;

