4. Pregnancy was recorded at the outpatient follow-up for patients with reproductive needs ;
5. Patients were routinely tested for blood routine (RBC, WBC, PLT, HGB), liver function (ALT, AST) and renal function (BUN, Cr), and recorded adverse events.

Note:

1. Basal follicle-stimulating hormone (FSH) $\geq 10\text{mIU/ml}$ at the first visit, and if other inclusion criteria are met if the patient has a history of testing with a baseline FSH $\geq 10\text{mIU/ml}$ in the past (interval > 4 weeks), he or she can be included in this study and drug therapy can be started; (Interval > 4 weeks) If the basic FSH $\geq 10\text{mIU/ml}$ has not been diagnosed, the patient is required to visit the hospital again after 4 weeks. If the basic FSH is still $\geq 10\text{mIU/ml}$, they can be included in this study and drug therapy

	
can be started.
 
2. For patients with regular menstrual periods, the basal FSH and antral follicle count (AFC) should be followed up on the 2nd to 4th day of the menstrual cycle. If the patient has menstrual cramps after the follow-up and has not exceeded the visit window, they are required to re-examine on the 2nd to 4th day of the menstrual cycle and record the examination data.

Study endpoint	
Primary endpoint : FSH, LH
 
Secondary endpoints :
 
(1) FSH, LH, E₂, T; (2) Antral follicle count (AFC); (3) Basal sex hormones and Anti- Mullerian hormone (AMH) on day 2/3 of the menstrual cycle; (4) Embryo laboratory indicators including number of eggs harvested, number of MII eggs, normally fertilized number, and number of good quality embryos; (5) Peripheral blood human villous gonadotropin (HCG); (6) Clinical pregnancy rate (patients with reproductive needs).

Security indicators	
1. Blood routine (RBC, WBC, PLT, HGB) , liver function (ALT, AST) and renal function (BUN, Cr) ;
 
2. Patient adverse events were recorded.

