Clinical Efficacy Analysis of Resveratrol in the Treatment of Primary Ovarian Insufficiency

Date: May 16, 2022

Research Proposal Summary

Statistical analysis

The case observation form completed by the test center was reviewed and returned by the project team of Reproductive Medicine Center, Affiliated Hospital of Nantong University, and the data was processed by a statistical analyst. The data in the case report form is entered in two copies, and the database is locked after verification and confirmation. SPSS26.0 software was used for statistical analysis. The full analysis set (FAS) and the per-protocol set (PPS) were used for effectiveness analysis, and the safety data set (SS) was used for safety analysis. Measurement data were expressed as mean±standard deviation ($\bar{x}\pm s$), multiple time points were compared by repeated measures analysis of variance, and pairwise comparisons were by Bonferroni test; enumeration data were expressed by the number of cases or percentages, and χ^2 was used. Test for statistical comparison. $P<0.05$ indicated that the difference was statistically significant.

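### The SAP sets no analysis scale and no baseline adjustment for FSH, LH and AMH: ANCOVA on baseline is a free gain in efficiency, and a log scale a conditional one

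*SAP*

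**What the plan says.** The Statistical analysis section of the SAP treats all continuous outcomes alike. "Measurement data were expressed as mean±standard deviation" is the summary, and "multiple time points were compared by repeated measures analysis of variance" is the test, with Bonferroni pairwise comparisons. No transformation, distribution check, rank-based alternative or baseline covariate is mentioned.

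The Study endpoint row of the Protocol lists "Primary endpoint : FSH, LH"; AMH is among the secondary endpoints. Hormones are measured before treatment and at 3 months.

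Inclusion criterion 1 requires "Amenorrhea or oligomenorrhea at least 4 months and two (>4 weeks interval) basal FSH" of at least 10 mIU/ml. None of the ten exclusion criteria removes high values. The diagnostic criteria describe premature ovarian failure, with "FSH>40IU/L, and decreased estrogen levels before the age of 40", as the final stage of the same disease, so such patients may enter. LH and AMH have no eligibility limit.

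**The concern.** Baseline FSH has a floor and an open right tail. If a patient's FSH also varies in proportion to its level, a few high values dominate the raw-scale variance, and the arithmetic mean describes few patients. The planned test also leaves the baseline value out as a covariate, although it is already collected. Both choices may cost power in a trial of fixed size. Because the SAP is silent on scale, the scale could also be chosen after results are seen.

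**Working it through.** **Inputs from the documents.** 150 patients (Protocol, "Total number of cases"), "randomly assigned to the RES group and non-RES group according to 1: 1", hence 75 per arm; two measurement times; significance at 0.05 (SAP; two-sided assumed, since sidedness is not stated); FSH floor of 10. SD, effect size, power, dropout and assay limits are not given, so everything distributional below is an assumption.

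**1. The plan's own figure.** 150 has no stated derivation and cannot be reproduced. Inverted, the detectable standardised difference is (z for alpha + z for power) × √(2/75):
- 80% power: (1.960 + 0.8416) × 0.1633 = 0.4575
- 90% power: (1.960 + 1.2816) × 0.1633 = 0.529

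**2. What the planned test amounts to.** With two times, the group-by-time test equals a t-test on change, which fixes the slope of follow-up on baseline at 1. ANCOVA estimates that slope. With equal SD σ and correlation ρ at both times, the variance of change is 2σ²(1−ρ) and the ANCOVA residual variance is σ²(1−ρ²). Their ratio is (1+ρ)/2, never above 1. Adjustment therefore costs at most one degree of freedom, and gains nothing when the slope is 1.

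**3. Proportional variability, 20% fall.** Log-normal FSH truncated at 10, median 15-30, between-patient log-SD 0.5-0.6, within-patient 0.3-0.4, skewness 2.0-2.5; four scenarios within those ranges, 3,000 trials each.

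| Scenario | Raw change | Raw ANCOVA | Log ANCOVA | Gain from covariate | Further gain from log |
|---|---|---|---|---|---|
| 1 | 75.6% | 86.7% | 93.8% | 11.1 | 7.1 |
| 2 | 49.2% | 63.6% | 74.8% | 14.4 | 11.2 |
| 3 | 70.8% | 82.6% | 92.4% | 11.8 | 9.8 |
| 4 | 79.2% | 89.1% | 93.5% | 9.9 | 4.4 |

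Repeat simulations under proportional variability gave 47-79%, 60-90% and 74-94%. Overall the covariate adds about 10-15 points and logging roughly 4-13.

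**4. Logging in isolation.** Here follow-up is baseline times random error, so the slope is close to 1 and ANCOVA matches change, as step 2 predicts. Ratio 0.85, median 25 before truncation, 2,000 trials each; analysis of change:

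| Baseline log-SD (skewness) | Within-patient 0.40: raw → log | Within-patient 0.25: raw → log |
|---|---|---|
| 0.3 (0.9) | 63% → 69% | 96% → 98% |
| 0.5 (1.6) | 55% → 69% | 93% → 97% |
| 0.7 (2.4) | 51% → 71% | 88% → 98% |

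**5. Additive effect, constant variability.** Same baselines, fall of 0.4575 × SD of change; ANCOVA, raw → log:

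| SD of change | log-SD 0.3 | log-SD 0.5 | log-SD 0.7 |
|---|---|---|---|
| 4 | 79.8% → 73.6% | 80.8% → 66.6% | 80.1% → 62.8% |
| 6 | 80.4% → 67.8% | 79.8% → 60.7% | 78.5% → 55.9% |
| 8 | 80.6% → 64.9% | 79.0% → 58.8% | 76.8% → 52.3% |

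The losses run from 6.2 points (79.8 − 73.6) to 24.5 (76.8 − 52.3). The larger ones probably owe something to follow-up values driven near zero, which the simulation set to 0.5. Other additive simulations lost 6-13 points; in one set (fall 3.5-4.5, error SD 6-8) raw ANCOVA had 68-76% and log ANCOVA 55-67%.

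**6. Additive effect, proportional variability.** With a 4 IU/L fall, log ANCOVA beat raw ANCOVA in all four scenarios: 96% v 75%, 65% v 28%, 65% v 33%, 45% v 17%. The loss in step 5 therefore comes from variability that does not grow with level, not from additivity alone.

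**7. Type I error.** 4.1-5.4% on both scales under the multiplicative null.

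**8. Low AMH values.** Assumed median 0.3, log-SD 1, within-patient log-SD 0.4, ratio 1.2; 3,000 trials. Without an assay limit, power is 40% raw and 79% log. With a limit of 0.06 (about 6% of follow-up values below it), it is 40% and 76% if low values are set to half the limit, but 42% and 43% if they are set to 0.001.

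**The case against.** The strongest objection is that a log-normal model with a proportional effect favours logs by construction. No document says how the effect scales, and step 5 shows the opposite sign. A reader might infer that logging recovers power at no cost; the documents do not support that. The gain is conditional, the estimand changes from a mean difference to a ratio of geometric means, and step 8 shows that a poor rule for low values can erase the AMH gain.

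Three further points stand:
- The entry floor concerns FSH at baseline only. It says nothing about LH or AMH, follow-up FSH is not truncated, and a log does not undo truncation. The argument is right skew, and the staging cut-offs are not data on how patients will be spread.
- The mean±SD sentence is about description. That the ANOVA is on raw values is inferred from silence, though it is the natural reading.
- Much of the contrast between the planned test and log ANCOVA comes from the covariate, not the log.

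One part does not stand. Additivity alone does not reverse the result (step 6); constant variability is also needed. For FSH ranging from 10 to above 40, proportional variability is a reasonable default, but the documents cannot confirm it.

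**Conclusion.** The point holds as one about efficiency and interpretation. It would be wrong to conclude that the planned analysis is invalid, since its error rate is sound.

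The firmer part is baseline adjustment: about 10-15 points of power over the two-time interaction under the assumptions of step 3, shrinking to nothing where the slope is near 1, with no material downside. The log scale is a sensible default for FSH and plausible for LH and AMH. It is worth roughly 4-13 further points if within-patient variability is proportional to level, and costs 6-13 points or more (up to about 25 in step 5) if the effect is additive with constant variability. The LH case was not simulated and rests on plausible skew alone.

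**What to change.** Amend the SAP before unblinding:
1. Make the primary between-group comparison an ANCOVA of the 3-month value with the baseline value as covariate, and say which pre-treatment reading is the baseline.
2. For FSH, LH and AMH, use natural logs of both the 3-month and baseline values. Report the RES/vitamin E geometric mean ratio with 95% CI.
3. State a rule for values at or below the assay limit (for example, half the limit, with counts by arm), and do not substitute near-zero values.
4. Keep the raw-scale ANCOVA as a prespecified sensitivity analysis, to cover the case in which the effect and variability do not scale with level.

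The cost is SAP text plus the low-value rule; no patients, visits or measurements are added. The downside is that results are read as ratios rather than IU/L differences, and that the gain from logging is not guaranteed.

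### The SAP names no between-arm test and no baseline covariate for FSH and LH; ANCOVA on the baseline value would be more precise at no cost in data

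*SAP*

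**What the plan says.** The protocol's Study endpoint row reads "Primary endpoint : FSH, LH", with no time point or summary measure. Under Trial grouping and medication, women are randomised 1:1, and basal sex hormones, which include FSH and LH, are measured "on day 2/3 of the menstrual cycle before treatment and 3 months after treatment". The total is 150, so 75 per arm.

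The SAP's Statistical analysis section is a single paragraph. For continuous data it says that "multiple time points were compared by repeated measures analysis of variance, and pairwise comparisons were by Bonferroni test". It sets significance at P<0.05. Neither document names a treatment factor, a group-by-time term or a baseline covariate, and neither gives a power calculation, SD, effect size or correlation.

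Other protocol text bears on which values enter the analysis:

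- **Entry.** The inclusion criteria ask for "Amenorrhea or oligomenorrhea at least 4 months and two (>4 weeks interval) basal FSH" values of at least 10 mIU/ml.
- **Baseline.** Note 1 under Treatment and follow-up lets one of the two qualifying values come from the woman's past record. Once the second is in hand, "he or she can be included in this study and drug therapy can be started".
- **Follow-up.** On the course itself: "Patients in group A received oral RES at 250mg daily for three months". Vitamin E is given for the same period in the other arm. Note 2 says that some women seen inside the visit window must return: "they are required to re-examine on the 2nd to 4th day of the menstrual cycle and record the examination data".

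**The concern.** The trial is randomised, so its efficacy claim should rest on a stated comparison of the arms. The SAP sentence describes a comparison of time points. A repeated-measures ANOVA with two arms produces three terms, and the plan does not choose among them:

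- **Group-by-time.** A valid randomised comparison, and the natural one here, but it does not make the best use of baseline.
- **Group main effect.** Averages the pre-treatment value with the 3-month value, which dilutes any effect. The text does not clearly point to it.
- **Time.** Not a randomised comparison. Because women are selected for high FSH, it would include some regression to the mean.

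The choice of primary test is therefore left to the analyst, possibly after the data are seen. Even the natural choice gives up precision at a fixed 150 women.

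The two values to be compared are also loosely defined. The last value before the first dose is the natural baseline, but the plan does not say so. The follow-up time could mean the end of the three-month course or three months after it. A woman recalled under Note 2 can have two follow-up FSH values, with no rule on which is analysed.

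**Working it through.** The plan has no figure to reproduce: 150 is stated without a derivation.

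**Inputs.** From the documents: 75 per arm (150 at 1:1), two scheduled hormone measurements, significance level 0.05. Assumed: two-sided testing, no dropout, SD of 1 at both visits, and a range for rho, the baseline to 3-month correlation.

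**Variance of each between-arm test**, relative to comparing 3-month values alone and scaled to the 3-month effect:

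- group-by-time (the same as a t-test on change): 2(1-rho)
- group main effect: 2(1+rho)
- ANCOVA on baseline: 1-rho²

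Efficiency of group-by-time against ANCOVA = (1-rho²)/[2(1-rho)] = (1+rho)/2.

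Detectable effect with 80% power = 2.80 × sqrt(2 × variance/75). At rho 0.5: 2.80 × sqrt(2 × 1.00/75) = 0.457 SD for group-by-time and 2.80 × sqrt(2 × 0.75/75) = 0.396 SD for ANCOVA.

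Power of group-by-time where ANCOVA has 80% = Phi(2.80 × sqrt(efficiency) - 1.96). At rho 0.5: Phi(2.43 - 1.96) = 68%.

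| rho | Efficiency | Group-by-time power when ANCOVA has 80% | Detectable effect in SD: group-by-time / ANCOVA / main effect |
|---|---|---|---|
| 0.3 | 0.65 | 62% | 0.541 / 0.436 / 0.738 |
| 0.5 | 0.75 | 68% | 0.457 / 0.396 / 0.792 |
| 0.7 | 0.85 | 73% | 0.354 / 0.327 / 0.844 |
| 0.9 | 0.95 | 78% | 0.205 / 0.199 / 0.892 |

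For an assumed effect of 0.4 SD at rho 0.3 / 0.5 / 0.7, power is 72.8 / 80.7 / 92.9% for ANCOVA, 54.4 / 68.8 / 88.5% for group-by-time and 33.0 / 29.3 / 26.4% for the main effect. Simulation with 4000 trials per value agreed to within 1 percentage point.

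**Direction without the equal-SD assumption.** With SDs s1 (baseline) and s2 (3 months), the change-score variance is s1² + s2² - 2·rho·s1·s2 and the ANCOVA variance is s2²(1-rho²). The difference is (s1 - rho·s2)², which is never negative. ANCOVA cannot have the larger variance, apart from the one degree of freedom it spends.

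**FSH under the two-value entry rule.** FSH was taken as log-normal with no drug effect, in 18 assumed settings: median 15, 20 or 25; between-person log-SD 0.4, 0.6 or 0.8; within-person log-SD 0.25 or 0.35. Women were kept if two values were at least 10, with the second as baseline. Limits carry a simulation error of about 0.01 in efficiency.

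- Raw rho ran from 0.43 to 0.86 and raw-scale efficiency from 0.75 to 0.93 (median 0.86). Log-scale efficiency was 0.80 to 0.96.
- On the raw scale, group-by-time has 68% to 77% power where ANCOVA has 80%. Its confidence interval is 4% to 15% wider (1/sqrt(0.93) = 1.04; 1/sqrt(0.75) = 1.15). The 150 women give the precision of 113 to 140 analysed by ANCOVA (150 × 0.75; 150 × 0.93).
- Type I error was near nominal for both: 3.9% to 5.6% for group-by-time and 4.3% to 5.9% for ANCOVA.
- Mean raw FSH fell by 0.3% to 4.0% from regression to the mean alone. A before-after test in one arm declared a fall in 3% to 10% of trials against a nominal 2.5%; pooling both arms, the range was about 2% to 15%.

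**The case against.** The strongest reply is that the plan contains no invalid test. In a two-arm 1:1 trial, leaving the factor's name out of a one-sentence summary does not show that no arm comparison was intended. Group-by-time is the obvious reading, it holds its type I error, and regression to the mean affects both arms alike. On that view the defect is one missing phrase, and ANCOVA is a preference worth a few points of power. Much of this stands: the gain is modest, and naming group-by-time would close the main gap. It does not remove the case for ANCOVA, which is at least as precise and uses only values already scheduled.

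A second reply is that the SAP speaks of multiple time points with Bonferroni pairwise comparisons, which do nothing when there are only two. If more visits were intended, (1+rho)/2 would not apply directly. That is fair, but the protocol schedules basal hormones only twice.

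A third is that the definitions can be inferred. Stimulation and egg collection are described after the course, which favours an end-of-course reading, and a correctly timed repeat would naturally replace the earlier value. These inferences are reasonable, but the plan does not state them. On their own they would be only missing detail.

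Finally, every size rests on assumed inputs. That is true, and it limits what can be said about magnitude but not about direction.

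**Conclusion.** The concern holds and should be fixed. The omission is certain: neither document names the between-arm test for FSH and LH or a baseline covariate. ANCOVA's precision advantage over group-by-time is also certain in direction. Its size depends on inputs that the documents do not give. For rho between 0.5 and 0.7 with equal SDs, group-by-time keeps 75% to 85% of ANCOVA's efficiency, and the detectable effect at 75 per arm is 0.46 rather than 0.40 SD, or 0.35 rather than 0.33 SD. The loss shrinks as rho rises or the true effect grows.

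Regression to the mean is a secondary point. It is small under the assumed FSH distributions, matters only if the time term or a within-arm change is read as efficacy, and does not bias a between-arm test. It is an FSH issue, since LH has no entry criterion of its own.

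**What to change.** In the SAP's Statistical analysis section:

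1. For each of FSH and LH, make the efficacy test the between-arm ANCOVA of the 3-month value on treatment and baseline, and report the adjusted difference with its 95% confidence interval.
2. Define baseline as the last value before the first dose.
3. State which date the 3-month value is counted from, and which value is analysed when a woman is re-examined under Note 2.
4. Make within-arm before-after changes descriptive.
5. If repeated-measures ANOVA is kept, name group-by-time as the treatment test.

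A log-scale analysis can be pre-specified as a sensitivity analysis. It should be primary only if the sponsor holds data showing right skew; the documents report none.

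The cost is a few lines of SAP text. ANCOVA runs in the SPSS package already named and needs no extra visits or patients. The change does not settle the choice between FAS and PPS, missing 3-month values, or how two primary endpoints each tested at 0.05 are combined; those need their own wording.

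### No named test clearly fits the four embryo counts and no covariate is named: adjusting for pre-treatment AMH would add power, and the pregnancy subset should be fixed before randomisation

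*SAP*

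**What the plan says.** **Methods.** The SAP (Statistical analysis) says that "multiple time points were compared by repeated measures analysis of variance", with Bonferroni pairwise comparisons. For categorical data it says that "enumeration data were expressed by the number of cases or percentages" and names the chi-square test. It names no single-occasion test, count model, covariate or stratification factor. Effectiveness is analysed in the FAS and the PPS, but the text defines neither.

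**Embryo counts.** The protocol (Study endpoint, secondary endpoint 4) lists "number of eggs harvested, number of MII eggs, normally fertilized number, and number of good quality embryos". Under Treatment and follow-up, after the stimulation steps, "a vaginal ultrasound-guided puncture was performed to collect eggs". One puncture is described; the number of cycles is not stated.

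**Baseline markers.** Under Trial grouping and medication, basal sex hormones and "anti-Muller tube hormone were administered on day 2/3 of the menstrual cycle before treatment and 3 months after treatment"; the verb must mean measured. For AFC the inspection list says only "The numbers of antral follicles (AFC) were recorded by B ultrasound transvaginal", so its pre-treatment timing is less explicit.

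**Pregnancy.** The inspection list says "Pregnancy was recorded at the outpatient follow-up for patients with reproductive needs", and secondary endpoint 6 reads "Clinical pregnancy rate (patients with reproductive needs" (closing bracket omitted). Secondary endpoint 5, blood HCG, carries no such limit. Elsewhere the protocol describes the groups as IVF patients and has every patient stimulated. No inclusion criterion concerns a wish for pregnancy.

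**The concern.** If the counts come from one retrieval, they have no pre-treatment value and nothing to repeat, so repeated-measures ANOVA does not apply directly. A count per woman is also not a number of cases or a percentage, so chi-square does not clearly apply either. The test, the handling of women without eggs, and any adjustment are therefore left to be chosen after the data are seen. A marker of ovarian reserve measured before treatment is likely to explain part of the variation in egg number, and the plan does not use it for these endpoints.

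For pregnancy, a subset defined by baseline intent gives a valid randomised comparison. A subset whose membership can change after allocation may not, if it changes differently between the arms. The only operational mention of this status is at outpatient follow-up, which comes after allocation.

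**Working it through.** **Inputs from the documents.** 150 women in total, allocated 1:1, so 75 per arm; four centres; significance at 0.05 (two-sided assumed). The documents give no power, effect size, SD, dropout, egg mean, marker correlation or pregnancy rate. The figure of 150 therefore cannot be reproduced, and every other input below is an assumption.

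**Step 1, closed form.** With 75 per arm, the detectable standardised difference at 80% power is (1.960 + 0.842) × √(2/75) = 0.457. Adjusting for a covariate with correlation r multiplies this by √(1 − r²): 0.436, 0.396 and 0.327 at r = 0.3, 0.5 and 0.7. At a true difference of 0.40, power is Φ(0.40 × √(75/2) / √(1 − r²) − 1.960), which is 68.8% unadjusted and 72.8%, 80.7% and 92.9% at the same three values of r.

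**Step 2, simulation for counts.** Negative binomial counts, dispersion 0.2, true ratio 1.4, marker slope 0.3, 0.4 or 0.5 per SD on the log scale, four centres with log-scale SD 0.1, 5,000 trials per setting. At means of 2 to 4 these slopes correspond to a marker–count correlation of about 0.32 to 0.57. Power, t-test v ANCOVA on marker and centre, no extra zeros:

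| Mean count | Slope 0.3 | Slope 0.4 | Slope 0.5 |
|---|---|---|---|
| 2 | 0.66 v 0.71 | 0.60 v 0.68 | 0.55 v 0.67 |
| 3 | 0.75 v 0.82 | 0.69 v 0.79 | 0.62 v 0.76 |
| 4 | 0.79 v 0.85 | 0.72 v 0.84 | 0.65 v 0.81 |

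The gain runs from 5 points (0.71 − 0.66) to 16 points (0.81 − 0.65). Type I error is 0.045 to 0.054 for both tests.

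**Step 3, lower means.** MII eggs, fertilised eggs and good embryos are subsets of the eggs, so their means cannot be higher and are probably lower. Over the same slopes the gain is about 4 to 11 points at mean 1.5, 2 to 6 at mean 1 and about 1 at mean 0.5.

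**Step 4, less favourable inputs.** At means of 2 to 4, 10% extra zeros cut the gain to 3 to 12 points and 20% cut it to 2 to 9. Without extra zeros, a slope of 0.2 gives +0.9 to +2.7 points, 0.1 gives −0.4 to +0.5, and an unrelated marker −1.0 to −0.2.

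**Step 5, the zero rule.** Same model, slope 0.4, no treatment effect, non-retrieval unrelated to response but always scored zero. ANCOVA then rejects in about 0.10 to 0.13 of trials when non-retrieval is 5% v 15% or 10% v 20% between the arms.

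**Step 6, pregnancy.** Let the true rate be 20% in both arms and let a share q of non-pregnant women leave the subset in one arm. That arm then shows 0.20/(1 − 0.80q):

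- q = 0.1: 0.20/0.92 = 21.7%, type I error 0.059
- q = 0.2: 0.20/0.84 = 23.8%, type I error 0.083
- q = 0.3: 0.20/0.76 = 26.3%, type I error 0.138

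These are chi-square results at 75 per arm. With 10% v 20% leaving, type I error is 0.060. With equal leaving in both arms it is 0.049 to 0.052, and with a subset fixed at baseline 0.052 to 0.053.

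**The case against.** With two arms and one occasion, the between-subject F test from an analysis of variance is the t-test. A natural reading of the SAP therefore gives a valid comparison, and an unnamed test or zero rule on a secondary endpoint is, taken alone, only missing detail. This stands. What remains is that a better method is available at almost no cost with a value already collected.

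The size of the gain rests wholly on assumed means, slopes and dispersion. This also stands: the upper figures apply to egg-like means and should not be read across to good-quality embryos.

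A reader might infer that the baseline data go unused altogether. They do not: basal hormones and AMH can enter the repeated-measures analyses of those same variables. They are unused only as covariates for the embryo counts, and naming a t-test would not change that.

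A reader might also infer that eggs will be pooled into a chi-square test as if independent. Under an assumed 2 to 3 eggs per woman and intraclass correlation 0.2 to 0.4, that would inflate type I error to about 7 to 14%. The SAP does not say this will be done.

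On pregnancy, no text says that intent may change after allocation, and because all patients are stimulated the subset may be nearly everyone. The point rests on silence, and the larger error rates need 20 to 30% of non-pregnant women to leave in one arm only.

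**Conclusion.** The concern holds as a recommended improvement to secondary analyses. The SAP names no between-group test that clearly fits the four counts, and no covariate, although AMH is measured before treatment. That the counts come from a single retrieval is inferred, since the number of cycles is not stated. The consequence is lost power, not invalidity: roughly 5 to 16 points at mean counts of 2 to 4, falling to about 1 point at mean 0.5, under a true ratio of 1.4, slopes of 0.3 to 0.5 and no extra zeros. The gain is smaller with extra zeros or a weaker marker. FSH and LH are not affected.

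The pregnancy part is secondary. It would be tempting to conclude that the pregnancy comparison is biased. The documents show only that the time of setting the status is not stated; a status set at baseline would be sound. Confidence is medium, because none of the inputs behind the magnitudes can be taken from the documents.

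**What to change.** **Embryo counts.** State in the SAP that each count is compared per randomised woman, in a defined FAS, at the first retrieval after treatment, by ANCOVA adjusted for pre-treatment AMH and centre. Allow AFC in place of AMH only if a pre-treatment value is confirmed.

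**Zero rule.** Score zero only when stimulation was started and no egg was obtained because of poor response, or when retrieval yielded none. Treat withdrawal, loss to follow-up and other non-retrieval unrelated to response as missing. State separately how conception before retrieval is handled.

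**Pregnancy.** Reconcile the protocol's description of IVF patients who are all stimulated with the restriction of the pregnancy endpoint. Record reproductive intent before randomisation and use that baseline-defined set as the denominator. Report the rate per randomised woman as a sensitivity analysis, supported by the HCG endpoint.

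**Cost.** A few SAP sentences, one baseline item, a recorded reason for each non-retrieval, and a rule for missing baseline AMH. ANCOVA is standard in SPSS. An uninformative marker costs at most about 1 point of power. The reported pregnancy rate may be slightly lower, because women who later change their mind stay in the denominator.
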